## Protocol Synopsis

**Title:** A Phase 2, Double-Blind, Randomized, Controlled Study to Evaluate the Efficacy and Safety of JointStem, Autologous Adipose Tissue Derived Mesenchymal Stem Cells, in Treatment of Osteoarthritis

**Phase:** Phase 2

**Indication:** Osteoarthritis (Degenerative Arthritis)

**Study Objective:** To evaluate the efficacy and safety of autologous adipose tissue derived mesenchymal stem cells (AdMSC) for the treatment of osteoarthritis

**Study Design:** This study is a double-blind, randomized, controlled study with two arms to evaluate JointStem as a treatment for subjects with osteoarthritis. Following a 2-week screening period, approximately 30 subjects will be randomly assigned into one of the following two arms in a 2:1 ratio (2 JointStem : 1 positive control):

- JointStem (1x10^8 cells/3mL)
- Positive control: Synvisc-One®

After each subject completes 6-month visit (Visit 6) and the data management team confirms all individual data have no issue, the individual database will be locked and the blinding will be open for the statistical analysis. Only subjects who are randomized to JointStem group will then be scheduled for 9-month and 12-month follow-up visits (Visits 7 and 8).

Long-term follow-up visit will be conducted to collect long-term feedbacks (records of medications and treatments) following 2 years after injection for all subjects who complete 6-month visit and accept the long-term follow-up visit.

**Co-Primary Endpoints:**  
① Change of WOMAC score from baseline at Month 6 (JointStem group)  
② Change of VAS score from baseline at Month 6 (JointStem group)  
③ MRI improvement evaluation at Month 6 (JointStem group)

**Secondary Endpoints:**  
1) JointStem group vs. positive control group  
① Change of WOMAC score from baseline at Month 6  
② Change of VAS score from baseline at Month 6  
③ Change of KOOS from baseline at Month 6  
④ Change of Lysholm Knee Scoring Scale from baseline at Month 6  
⑤ Change of IKDC from baseline at Month 6  
⑥ Change of RAND-36 Score from baseline at Month 6  
2) JointStem group  
① Change of WOMAC score from baseline at Months 9 and 12  
② Change of VAS score from baseline at Months 9 and 12  
③ Comparison of MRI improvement evaluations between at Month 6 and at Month 12  
④ Change of Lysholm Knee Scoring Scale from baseline at Months 6, 9 and 12  
⑤ Change of KOOS from baseline at Months 6, 9 and 12

- ⑥ Change of IKDC from baseline at Months 6, 9 and 12
- ⑦ Change of RAND-36 Score from baseline at Months 6, 9 and 12
- 3) Incidence of adverse events and laboratory abnormalities

**Exploratory Endpoints:** Analysis of all efficacy scales and MRI results and the history of treatments and medications following 2 years after injection for all subjects who are injected and complete 6-month follow-up visit

**Inclusion Criteria:**

- 1) Subject who can give written informed consent
- 2) Male or female of any race, aged 22-60
- 3) Subject who had osteoarthritis of knee diagnosed at least six months prior to Screening
- 4) Subject who has joint pain  $\geq$  40mm on VAS (Visual Analog Scale) at Screening
- 5) Subject who has swelling, tenderness and active range of motion  $\geq$  Grade I at Screening
- 6) Subject who seeks invasive interventions of intra-articular injections
- 7) Subject who is willing to discontinue all pain medications for osteoarthritis except rescue medication (< acetaminophen 3.25 g per day) at least 72 hours prior to screening and throughout the duration of study
- 8) Subject who has radiographic evidence of grade 3 to 4 osteoarthritis based on the Kellgren and Lawrence radiographic criteria.
- 9) Female subject who meets one of the following criteria:
  - a. Female subject of non-childbearing potential:
    - Post-menopausal for at least 6 months; or
    - Surgically sterile
  - b. Female subject of child-bearing potential:
    - Neither pregnant nor lactating; and
    - Abstinent or use adequate contraception (2 forms of birth control, one of which must be a barrier method)
- 10) Subject who is able to comply with lifestyle guidelines, scheduled visits, treatment plan, laboratory tests, and other study procedures

**Exclusion Criteria:**

- 1) Subject who has Body Mass Index (BMI)  $> 35 \text{ kg/m}^2$
- 2) Subject who has unstable knees
- 3) Subject who took any NSAIDs within two weeks from Screening
- 4) Subject who had any intra-articular injection therapy in any joint within 2 months from Screening
- 5) Subject who has any clinically significant disease, which is judged by the investigator to affect this clinical trial, including but not limited to diabetes not adequately controlled, bleeding diathesis or hematologic disease, endocrinopathies, cardiovascular disease, renal disease (severe renal impairment), autoimmune disease, inflammatory arthritides, and current infectious disease
- 6) Subject who has inflammatory arthropathy (rheumatoid, psoriatic, or avascular necrosis), and post traumatic or septic arthritis
- 7) Subject who has chondrocalcinosis, Paget's disease, Villonodular synovitis, and other non-OA joint diseases
- 8) Subject who has HIV/viral hepatitis
- 9) Subject who had knee surgery or radiation therapy in the affected joint within 6 months from Screening
- 10) Subject who had CVA attack within 6 months from Screening
- 11) Subject for whom the investigator judges the liposuction can cause any problems

- 12) Subject who has significant lab abnormalities for the following parameters (If the value is within 10% of the listed laboratory exclusion criterion value and the value is considered not to be clinically significant by the investigator, the subject can be considered for enrollment):
  - Serum ALT and AST > 2 x upper limit of normal
  - Serum creatinine out of normal range
  - PT/INR out of normal range
  - Hemoglobin < 10 g/dL for female subject and hemoglobin < 11 g/dL for male subject
  - Platelets out of normal range
- 13) Subject who has history of local anesthetic allergy
- 14) Subject who took immunosuppressants such as Cyclosporin A or azathioprine within 6 weeks from Screening
- 15) (If a subject uses aspirin or plavix) Subject for whom it is determined that it would not be safe to stop the aspirin/plavix therapy for 2 weeks prior to Visit 2
- 16) Subject who uses anticoagulants which cannot be stopped or corrected
- 17) Subject who had oral or intra-muscular corticosteroids within 30 days from Visit 2
- 18) Subject who had intra-articular corticosteroid injection in any joint within 30 days from Visit 2
- 19) Subject who had intra-articular hyaluronic acid injection within 30 days from Visit 2
- 20) Subject who has known hypersensitivity (allergy) to hyaluronan (sodium hyaluronate) preparations
- 21) Subject who has knee joint infections or skin diseases or infections in the area of the injection site
- 22) Subject who is an active drug/EtOH abuser
- 23) Subject who was enrolled in any other clinical trials within 2 months from Screening
- 24) Subject who the principal investigator considers inappropriate for the study due to any other reasons than those listed above
- 25) Subject whose MRI scan results during the screening period do not demonstrate any sign of cartilage damage.

**Investigational Product Dosage and Administration:**

One of two treatment groups will receive a single injection of JointStem ( $1 \times 10^8$  cells/3mL, autologous adipose tissue derived mesenchymal stem cells) via intra-articular injection.

**Control Group:**

Positive control (Synvisc-One®) via intra-articular injection

**Study Procedures:**

Visit 1 (Week -7) – Screening  
Visit 2 (Week -5) – Harvest of Adipose Tissue  
Visit 3 (Week 0) – Baseline (intra-articular injection)  
Visit 4 (Month 1) – 1-month follow-up  
Visit 5 (Month 3) – 3-month follow-up  
Visit 6 (Month 6) – 6-month follow-up (completion of treatment)  
\* *Double-blinding will end individually.*  
Visit 7 (Month 9) – 9-month follow-up (for only JointStem group)  
Visit 8 (Month 12) – 12-month follow-up (for only JointStem group)  
Long-term Follow-up (Month 24) – 24-month follow-up

**Statistical Analysis:**

1. Co-primary Endpoints

Using the following three co-primary efficacy variables, the joint functional improvement of knee joint will be evaluated and gatekeeping procedures will be used for these three hypothesis tests.

- 1) Change of WOMAC score from baseline at Month 6 (JointStem group)  
It will be tested using paired t-test (one-sided test,  $\alpha=0.05$ ). If change of WOMAC score from baseline at Month 6 doesn't satisfy normal distribution, Wilcoxon signed rank test will be performed.
- 2) Change of VAS score from baseline at Month 6 (JointStem group)  
It will be tested using paired t-test (one-sided test,  $\alpha=0.05$ ). If change of VAS score from baseline at Month 6 doesn't satisfy normal distribution, Wilcoxon signed rank test will be performed.
- 3) MRI improvement evaluation at Month 6 (JointStem group)  
The frequency and percentage of subjects whose final PI evaluation is 'improvement' will be calculated (validity criteria: 36%).

## 2. Secondary Endpoints

The comparison of WOMAC score, VAS score, Lysholm Knee Scoring Scale, KOOS, IKDC and RAND-36 score between study and control groups will be analyzed using Analysis of Covariance (ANCOVA) with factors of treatment and baseline of each variable as a covariate.

Model-based LS Means of the differences between study and control groups along with 95% CI and p-value will be provided.

In addition, the change of secondary efficacy variables within study group shall be tested using paired t-test. If the change of score from baseline at each assessment point doesn't satisfy normal distribution, Wilcoxon signed rank test will be performed.

In case of MRI, the frequency and percentage of subjects whose PI evaluation is 'improvement' at Month 6 will be calculated. In addition, MRI improvement evaluation at Month 12 compared to Month 6 will be analyzed using McNemar test or Bowker's test.

Safety variables will be summarized descriptively, by treatment group and visit.

When at least 15 subjects complete 6-month visits (Visit 6, Month 6), one unblinded interim analysis can be performed to evaluate the efficacy and safety of JointStem without the suspension of subject's schedule of assessments. The details of this interim analysis will be presented in the statistical analysis plan.

All efficacy variables and the history of treatments and medications, which are measured at a long-term follow-up visit (24 months after injection) will be analyzed between treatment groups to see any long-term effects of JointStem. Also, MRI results of long-term follow-up visit will be compared to previous MRI results to see any long-term effects of JointStem.

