### 2.2 Current Treatment for Osteoarthritis and Their Pitfalls

The cartilage is a unique avascular, aneural tissue that has limited capacity of self-repair once damaged. Despite ongoing research, treatments to manage the disease remain merely symptom-relieving, designed to control pain, and improve function and quality of life limiting adverse events. An effective treatment for cartilage defects is yet to be discovered.

Treatment generally involves a combination of lifestyle modification, analgesics, nonsteroidal anti-inflammatories, and joint injections with steroids or hyaluronan (lubricant). If pain becomes debilitating, joint replacement surgery may be used to improve the quality of life, e.g. partial joint resurfacing (hip and shoulder), and total joint replacement (hip and knee).Conaghan 2008 Although various treatments are currently in use, none of them is to address the root of cause—cartilage regeneration. In other words, there has been no cure for osteoarthritis till today.

As a way of regenerating the damaged or defective cartilage tissue, treatment of localized damage to articular cartilage using autologous chondrocytes is currently under review. A few studies are marketing this method of treatment named “autologous chondrocyte transplant”.Wysocka 2010, Hahn 2010 The treatment involves the extraction of healthy cartilage tissue from the patient which is then cultured and transplanted into the damaged site. However, this treatment requires the extraction of

chondrocytes directly from the patient and thus causes new damages in healthy articular cartilage. Also, “autologous chondrocyte transplant” cannot be applied to large lesions. Moreover, the effect is not satisfactory in patients over 40 years old whose cellular regeneration is slowed-down due to aging.

Thus, autologous chondrocyte transplant is rather limited in the number of cells harvested and their activation level and is therefore restricted in terms of treatment site, severity of the condition, and the size of lesion. Generally speaking, there was no therapy available till today to regenerate cartilage for adult.

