#### **Screening Visit 1 (Week -7)**

The following screening assessments/procedures must be performed and the results documented within approximately 7 weeks before Baseline visit unless otherwise indicated:

- Record demographic data (i.e., date of birth, race, height, and weight).
- Measure VAS (see Appendix 4).
- Record medical and medication history.
- Perform a complete physical examination.
- Measure vital signs (sitting blood pressure, pulse, breathing, and temperature).
- Measure 12-lead ECG.
- Collect blood and urine samples for hematology, serum chemistry, and urinalysis.
- Perform X-ray for Kellgren-Lawrence scale (see Appendix 2).
- Perform MRI to measure damaged cartilage area (Please follow the instruction separately provided by the sponsor). \* MRI may be performed the day of Visit 2 or after due to scheduling or re-scanning, as long as the results are confirmed prior to injection.

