## **6.2 Determination of Sample Size**

There was no formal sample size calculation since this is a proof-of-concept study and is not a hypothesis-driven study. The number of enrolled subjects is predefined at n=30, for 20 subjects per study group and 10 subjects per control group.

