4. DEMOGRAPHICS AND BASELINE CHARACTERISTICS

4.1 DEMOGRAPHICS AND BASELINE CHARACTERISTICS

Demographic data (age, gender, race, and ethnicity) and baseline characteristics (including height, weight and body mass index (BMI)) collected at study screening will be summarized using descriptive statistics by treatment group and total for the ITT population.

A subject data listing of demographics and baseline characteristics will be provided.

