6.2 SECONDARY EFFICACY ANALYSIS

6.2.1 WOMAC Score

WOMAC score will be collected at Visits 3, 4, 5, 6, 7 and 8 (Baseline, M1, M3, M6, M9 and M12) or Early Termination (only if the subject is early terminated after Visit 3) or Final Follow-up Visit. Summary statistics of WOMAC score will be presented by visit and treatment group. The change from baseline will also be calculated and represented in summary table.

① Change of WOMAC score from baseline at Month 6 (JointStem group vs. positive control group)

This secondary efficacy endpoint will be analyzed with an ANCOVA with factors of treatment and the baseline of WOMAC score as a covariate. Model-based LS Means of the differences between study and control groups, along with 95% CI and p-value will be provided.

② Change of WOMAC score from baseline at Months 9 and 12 (JointStem group)

Change of WOMAC score from baseline at Months 9 and 12 will be analyzed using paired t-test (two-sided test, $\alpha=0.05$) with the null hypothesis equal to zero. The number of patients, mean, standard deviation, minimum (min) and maximum (max) values for the baseline, months 9, months 12 and change from baseline will be calculated and reported in summary table. The p-value will also be provided. Shapiro-Wilks test will be used to test the normality of change of WOMAC score from baseline at Months 9 and 12. If change of WOMAC score from baseline at Months 9 and 12 doesn't satisfy normal distribution, Wilcoxon signed rank test will be performed.

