6.2.2 VAS Score

VAS score will be collected at Visits 3, 4, 5, 6, 7 and 8 (Baseline, M1, M3, M6, M9 and M12) or Early Termination (only if the subject is early terminated after Visit 3) or Final Follow-up Visit. Summary statistics of VAS score will be presented by visit and treatment group. The change from baseline will also be calculated and represented in summary table.

- ① Change of VAS score from baseline at Month 6 (JointStem group vs. positive control group)

This secondary efficacy endpoint will be analyzed with an ANCOVA with factors of treatment and the baseline of VAS score as a covariate. Model-based LS Means of the differences between study and control groups, along with 95% CI and p-value will be provided.

- ② Change of VAS score from baseline at Months 9 and 12 (JointStem group)

Change of VAS score from baseline at Months 9 and 12 will be analyzed using paired t-test (two-sided test, $\alpha=0.05$) with the null hypothesis equal to zero. The number of patients, mean, standard deviation, minimum (min) and maximum (max) values for the baseline, months 9, months 12 and change from baseline will be calculated and reported in summary table. The p-value will also be provided. Shapiro-Wilks test will be used to test the normality of change of VAS score from baseline at Months 9 and 12. If change of VAS score from baseline at Months 9 and 12 doesn't satisfy normal distribution, Wilcoxon signed rank test will be performed.

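### The Month 6 between-arm ANCOVAs leave out Kellgren-Lawrence grade, which is obtained before randomization, so a chance imbalance in grade would be neither adjusted for nor, as the SAP stands, named for tabulation

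*Protocol*

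**What the plan says.** The Protocol Synopsis (Statistical Analysis, Secondary Endpoints) states that WOMAC, VAS, Lysholm, KOOS, IKDC and RAND-36 "will be analyzed using Analysis of Covariance (ANCOVA) with factors of treatment and baseline of each variable as a covariate". Protocol 6.1.5 repeats this scale by scale. The SAP does the same: for WOMAC (6.2.1), "This secondary efficacy endpoint will be analyzed with an ANCOVA with factors of treatment and the baseline of WOMAC score as a covariate"; for VAS (6.2.2) the analysis is "with an ANCOVA with factors of treatment and the baseline of VAS score as a covariate"; and 6.2.4 to 6.2.7 follow the same pattern. Neither document plans a model with further covariates.

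Entry requires "radiographic evidence of grade 3 to 4 osteoarthritis based on the Kellgren and Lawrence radiographic criteria", so there are two possible grades. Protocol 4.1 schedules the X-ray for grading at Visit 1, and 4.2.1 places randomization at Visit 2. Appendix 2 separates the grades by the extent of joint space narrowing, sclerosis and bone-end deformity.

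SAP 4.1 lists age, gender, race and ethnicity as demographics, and says that "baseline characteristics (including height, weight and body mass index (BMI)) collected at study screening will be summarized". K-L grade is not named. Protocol 6.1.2 lists demographics, medical history, treatment duration and baseline efficacy variables, and relies on randomization for balance. On size, Protocol 6.2 says: "The number of enrolled subjects is predefined at n=30, for 20 subjects per study group and 10 subjects per control group". The randomization instruction is a separate document.

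**The concern.** The three co-primary endpoints are within-arm. The Month 6 ANCOVAs are therefore the only between-arm efficacy tests with a specified model, and any statement about JointStem relative to hyaluronic acid rests on them.

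With 10 controls, a few more grade 4 knees in one arm make a sizeable difference in structural severity. A patient-reported baseline score carries only part of that information. WOMAC, Lysholm, KOOS, IKDC and RAND-36 are also first measured at Visit 3, after randomization and liposuction, whereas K-L grade is fixed before allocation. If grade is related to change, an imbalance moves the estimated difference, the planned model does not correct it, and a reader of the listed baseline characteristics would not see it. Adding the grade after codes are opened would be post hoc.

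**Working it through.** **Inputs from the documents.** N = 30, split 20/10 (Protocol 6.2; 2:1 of 30 gives 20 and 10). One baseline covariate per model, so residual df = 30 − 3 = 27. Two K-L grades. There is no stated power, effect size or SD to reproduce, because Protocol 6.2 says that no formal sample size calculation was made.

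**Assumptions (not in the documents).** K = number of grade 4 subjects among the 30, taken from 9 to 21. d = difference in change between grades after adjustment for own baseline, in residual SD units, taken from 0 to 1.0. Allocation not stratified by grade.

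**1. Chance of imbalance.** If x of the 10 controls are grade 4, the arm difference in grade 4 share is x/10 − (K − x)/20 = (3x − K)/20, and x is hypergeometric (30, K, 10). A difference of 30 points or more means |3x − K| ≥ 6.

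| K | P(≥ 30 points) | P(> 30 points) |
|---|---|---|
| 9 or 21 | 20.4% | 3.0% |
| 10 or 20 | 10.1% | 10.1% |
| 11 or 19 | 10.8% | 10.8% |
| 12 or 18 | 23.5% | 4.5% |
| 13 or 17 | 11.9% | 11.9% |
| 14 or 16 | 12.2% | 12.2% |
| 15 | 24.5% | 5.0% |

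Exactly 30 points is attainable only when K is a multiple of 3, which is why the middle column jumps. For K = 15, x = 3 gives 30% versus 60%, and x = 7 gives 70% versus 40%. The fair summary is about 10% to 25%.

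**2. Effect on the estimate.** SE of the difference = √(1/20 + 1/10) = 0.387 SD. A 30-point imbalance shifts it by 0.30 × d:
- d = 0.5: 0.15 SD, or 0.15/0.387 = 0.39 SE
- d = 1.0: 0.30 SD, or 0.30/0.387 = 0.77 SE

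**3. Type I error.** In a simulation with 10,000 trials per scenario, 20/10 allocation and severity terms omitted from the model, the planned ANCOVA rejected a true null in 4.7% to 5.4% of trials. The imbalance matters for the one estimate observed, not for the test over repeated randomizations.

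**4. Cost and gain of adding K-L grade.** The expected variance factor for p covariates is 1 + p/(N − p − 3). For p = 1 it is 1 + 1/26 = 1.0385; for p = 2 it is 1 + 2/25 = 1.08; the ratio is 1.04. With grades split evenly, grade explains R² = 0.25d²/(1 + 0.25d²), so the variance ratio is 1.04/(1 + 0.25d²).

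| d | Variance ratio |
|---|---|
| 0 | 1.040 |
| 0.3 | 1.017 |
| 0.4 | 1.000 |
| 0.5 | 0.979 |
| 0.8 | 0.897 |
| 1.0 | 0.832 |

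Break-even is 0.25d² = 0.04, so d = 0.4 (R² = 3.8%; 4.2% on interval width once the t quantile on 26 df is used). At d = 0 the 95% interval is about 2% wider.

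**The case against.** The case for leaving the plan alone is reasonable. ANCOVA on own baseline is a standard pre-specified model and already captures part of severity. These are secondary endpoints in an unpowered proof-of-concept study, where 30 subjects limit the comparison far more than the covariate list does: the detectable difference at 80% power is (1.960 + 0.842) × 0.387 = 1.09 SD before adjustment. No document gives a K-L effect on change, and entry restricts the grade to two adjacent levels. The SAP 4.1 list is introduced by an inclusive word, so it is not closed. Stratification cannot be ruled out, because the randomization instruction is not among these documents. All of this stands, and it makes the point a modest one.

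It also limits what a reader might infer:

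- *That the planned model loses precision.* Not shown. Below about d = 0.4 the added factor costs precision.
- *That the comparison is biased or its test invalid.* Chance imbalance does not do that, as step 3 shows.
- *That these are the only randomized comparisons.* An exploratory between-group analysis at Month 24 is planned (Protocol 6.4), though these documents specify no model for it.
- *That the protocol itself shows severity to drive response.* Section 2.2 calls a treatment "restricted in terms of treatment site, severity of the condition, and the size of lesion", but that treatment is autologous chondrocyte transplant, not JointStem.
- *That the Visit 1 VAS should also be used, by averaging it with the Visit 3 VAS as the covariate.* The outcome is change from Visit 3. Once the Visit 3 value itself leaves the model, its contribution to the change score is no longer fully removed. With VAS simulated at mean 55 and SD 20, Visit 1 truncated at the 40 mm entry limit, and correlations from 0.35 to 0.9 (all but the 40 mm limit assumed), residual variance was 1.02 to 1.26 times that of the planned model in all seven settings. A gain appears in most settings if the Month 6 score rather than the change is regressed on the mean, but that is not the planned outcome. The Visit 3 baseline should stay.

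**Conclusion.** The point holds as a cheap improvement, not as a flaw that invalidates the comparison. The Month 6 between-arm models omit a structural severity grade that is obtained before randomization, and the SAP does not name it for tabulation. If allocation is not stratified by grade, an arm difference of 30 points or more has a chance of about 10% to 25% for 9 to 21 grade 4 subjects out of 30. The upper end applies only at counts where exactly 30 points is attainable. Such an imbalance would move the estimate by about 0.4 to 0.8 of a standard error if the grades differ by 0.5 to 1.0 SD in change, which is an assumption.

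The argument for adjusting is protection of the estimate against an imbalance that may occur, with any gain in precision conditional on the grade effect. The worst-case price, about 4% in variance, is small against that.

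**What to change.** In Protocol 6.1.5 (with the matching Synopsis text) and in item 1 of SAP 6.2.1, 6.2.2 and 6.2.4 to 6.2.7, pre-specify K-L grade (3 or 4) as an added factor in the Month 6 ANCOVAs. Keep the Visit 3 value of the same scale as the covariate in every model, including VAS. State that the factor is dropped if only one grade is represented. In SAP 4.1, add K-L grade by arm to the baseline table.

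The cost is wording in both documents, one residual degree of freedom (27 to 26), and up to about 4% more variance if grade is unrelated to change. No new assessment is needed, but it should be confirmed that the grade is held as analysis data and not only as an eligibility check. Because codes open subject by subject after Visit 6, the change has to be fixed before the first code is opened to count as fully pre-specified; if it comes later, its date should be reported.
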